## STATISTICAL ANALYSIS

### Functional connectivity magnetic resonance imaging (fcMRI)

fcMRI will be performed as described in our previous publications. During fcMRI, participants will either be at rest or receiving a pain stimulus via a pressure cuff applied to the left lower leg evoking tonic pressure with pain of 40 on a 100 point numerical rating scale (0=no pain; 100=worst pain imaginable). This sustained pain is relevant to deep musculoskeletal clinical pain and can be applied for long durations (i.e. minutes) without tissue damage. Data will be corrected for physiological effects such as cardio-respiratory fluctuations that are known to influence fcMRI estimation. Resting connectivity network analysis will be performed using the FSL (FMRIB's Software Library, [www.fmrib.ox.ac.uk/fsl](http://www.fmrib.ox.ac.uk/fsl)) software package. All data will be corrected for motion artifacts, smoothed (FWHM 5 mm), and high-pass temporal filtered ( $f = 0.006\text{Hz}$ ). ICA Approach. The within- and between-subject resting fMRI data analysis will be performed using ICA through Multivariate Exploratory Linear Optimized Decomposition into Independent Components (MELODIC, an FSL tool) and a previously validated dual regression approach. We will apply probabilistic ICA to identify global, independent patterns of functional connectivity existent in the entire subject population. The number of independent components will be limited to 25 to reduce subcomponents. Networks of interest will be selected and the spatial independent component maps identified from the population data will be used as a spatial regressor in a general linear model of the subject's resting fcMRI data. This will allow us to estimate subject-specific spatial maps for each component. These maps will then be passed up to group analysis. Seed-voxel Approach: We will evaluate functional connectivity using seed-voxels from brain regions previously shown to be involved in consciousness or pain. The average time course in these regions will be used as regressors in a whole brain general linear model to find other brain regions also correlated with the seed region. A whole brain general linear model will be performed using the seed time course, averaged over a 3 mm radius sphere, as the regressor of interest. The resulting single subject maps will be normalized to standard space and passed up to group analyses. fcMRI group analyses: Nitrous oxide effects on brain connectivity will be estimated using a factorial model with treatment (nitrous versus placebo) and time (pre versus post) as factors. All statistical maps will be corrected for multiple comparisons on the cluster level  $p < 0.05$ , derived from an uncorrected  $p < 0.001$  on the voxel level.

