Preliminary Studies: We have shown previously that fibromyalgia patients display increased resting state connectivity between pain regions such as the insula and other non-pain related areas such as the DMN. Moreover, reductions in this connectivity were associated with reductions in clinical pain: the degree of this connectivity was directly correlated with clinical pain ratings. In our *Anesthesiology* article, we examined the effect of pregabalin, an efficacious analgesic, on chronic clinical pain in fibromyalgia. Prior to and following each treatment period (drug/placebo), patients underwent fcMRI of the entire brain during rest. We placed a seed voxel within the posterior insula, a region where we previously observed elevated glutamate in chronic pain patients, and we assessed connectivity of this structure to the DMN before and after pregabalin and placebo. Interestingly, we found that during pregabalin treatment, but not placebo, patients displayed decreased insula connectivity to the inferior parietal lobule (IPL; a DMN region), which was paralleled by reductions in clinical pain: patients with greater reductions in insula-DMN connectivity displayed greater analgesia. *These findings are relevant to the proposed study because*

*they demonstrate that we can measure changes in brain networks during pharmacologic treatment and these changes are related to analgesic drug action.*

[figure not shown]

Figure above shows that change in connectivity between the posterior insula and IPL correlates with change in spontaneous clinical pain. We acknowledge that network perturbation by nitrous oxide may involve other brain regions and networks.

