## SPECIFIC AIM

1. To identify dose-dependent changes in brain networks using fMRI studies in healthy volunteers receiving nitrous oxide.
2. To identify dose dependent changes in brain feedback connectivity using EEG in healthy volunteers receiving nitrous oxide.

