### **Consent/Pre-Scan Visit**

The study coordinator will determine whether the volunteer meets inclusion and does not meet exclusion criteria prior to consent. Following consent, each volunteer will complete a resting state questionnaire and QST familiarization/training during EEG acquisition. MR-compatible EEG cap and electrodes will be affixed to the participant's scalp to monitor brain activity during QST training. QST will consist of a constant pressure applied to the lower leg and/or visual stimulus outside of the scanner. Following each stimulus, participants will rate the pain intensity (0 = "no pain, 100 = "worst pain imaginable") and pain unpleasantness (0 = "neutral", 100 = "extremely unpleasant"). Participants will be

asked to complete another resting state questionnaire following training on simultaneous visual stimulus and pressure cuff. During this visit, participants will also be seen briefly by an anesthesiologist for an airway assessment to check for eligible Mallampati 1 or 2 airways.

Scanning Visit

Simultaneous Functional Magnetic Resonance Imaging/Electroencephalogram (fMRI/EEG)

Each volunteer will participate in one scanning visit in which simultaneous fMRI/EEG data will be collected wherein they receive placebo (20 minutes) followed by inhaled nitrous oxide at analgesic levels (35% inhaled concentration) over 40 minutes, then a nitrous oxide dose consistent with anesthetic-induced unconsciousness (70%) for 15 minutes [See Figure 1];

[figure not shown]

Figure 1. Study design schematic

Upon arrival, participants will complete baseline questionnaires (Part 1a). Prior to drug exposure, volunteers will be given an altered states of consciousness (ASC) questionnaire followed by a baseline resting state fMRI scan. During the placebo period, fMRI data will be acquired during additional tasks: visual stimulation task, evoked pressure pain applied to the lower leg induced by a cuff/automated tourniquet, and a combination visual stimulation and pressure pain cuff task. These scans will be repeated during both analgesic and anesthetic doses of nitrous oxide. End-tidal nitrous oxide concentrations will be assessed by standard gas analyzers during spontaneous ventilation through a secured face mask with tight seal.

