All subjects will have MR-compatible EEG electrodes affixed to their scalp for monitoring during the study. Participants will first complete an altered states of consciousness questionnaire. Continuous EEG will be acquired during a baseline (rest) period followed by three additional tasks mentioned previously.

For each participant, these tasks will be repeated at a low dose of nitrous oxide that is normally associated with analgesia (35% inhaled concentration) and a higher dose of nitrous oxide that is associated with anesthesia. Following administration of the analgesic dose of nitrous oxide, participants will be asked to complete a questionnaire to assess altered states of consciousness. Each testing session will conclude with a 15-minute continuous EEG acquired during the participant's recovery of consciousness. Following testing, the participants will be asked to complete an altered state of consciousness questionnaire.

To maximize safety, nitrous oxide will be delivered using MRI-compatible anesthesia machines at the University of Michigan hospital, and anesthetic doses of nitrous oxide will be administered outside of the scanner, where airway patency and physiological stability will be established prior to imaging the state of anesthetic-induced unconsciousness. At least two fully-trained anesthesiologists will direct all anesthetic administration. In order to maximize clinical monitoring during emergence, recovery from anesthetic doses will occur outside of the MRI scanner as well. All participants will receive ondansetron (4mg IV) with an additional dose of dexamethasone (4mg IV) if needed to prevent nausea and vomiting. In addition, glycopyrrolate (0.42-0.4 mg IV), labetalol (5-10 mg/kg IV), and midazolam (1-2 mg IV) will be available for use to mitigate any side effects, as needed. Also, standard intraoperative monitors (electrocardiogram, pulse oximetry, capnography) will be used.

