## **DATA COLLECTION**

Resting State Functional Connectivity (fcMRI).

During fcMRI, participants will either be at rest or receiving a pain stimulus via a pressure cuff applied to the left lower leg evoking tonic pressure with pain of 40 on a 100-point numerical rating scale (See below; 0=no pain; 100=worst pain imaginable). Functional connectivity fMRI will be performed on a 3 Tesla Philips Achieva (Best, Netherlands) using a T2\* weighted echo-planar sequence with the following parameters: TR/TE = 2000/30ms, flip angle=90°, FoV = 200x200mm, 48 AC-PC aligned slices, slice thickness 3 mm, scan time = 6min. These data will be analyzed using two approaches: a model-free independent component analysis (ICA) and seed-voxel based method (from evoked pain fMRI; See below).

Evoked pressure pain with blood pressure cuff:

Calibrated cuff pain stimuli will be delivered to the gastrocnemius area of the dominant leg using a validated cuff pain device that has been recently adapted to the MRI scanning environment. A computer controlled air compressor (Hokanson Rapid Cuff Inflator) will inflate the cuff to a pre-specified pressure, and maintain the pressure at that level. Subjects will participate in one test session of cuff pain prior to the EEG and the fMRI session. Pressure pain will be applied for a continuous 6-minute period three times during the fMRI protocol to evaluate functional brain connectivity response to deep pain (see below). One advantage to using cuff algometry pain is that unlike more superficial methods (e.g. heat pain), cuff pain responses are unaffected by sensitization or desensitization of the skin, indicating that this procedure primarily assesses sensitivity in muscle and other deep tissues. We have considerable experience applying these techniques in both healthy adults and chronic functional pain patients, and have found that all subjects are able to tolerate these procedures without any lasting discomfort.

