
### Network Analysis

In terms of network properties to be analyzed, the **degree** is the number of connections a node (in this case, a given brain region) has, while the **modularity** is a measure of the extent to which the connected regions form individual functional modules. We will first investigate the characteristic modules

corresponding to different states, then quantify the modularity of the networks. High-degree **hubs** facilitate “shortcuts” of network information transmission (much like a hub airport facilitates travel shortcuts) and are identified with the measures of *centrality* in a network. The centrality of a node measures its relative ability to integrate information globally within a brain network. We will assess several centrality measures (degree centrality, closeness centrality, betweenness centrality and Eigenvector centrality) to test the robustness of the hub structure. The **average path length**, which measures the mean number of steps along the shortest paths for all possible pairs of network nodes, will be used for quantifying the **global efficiency** of brain networks (since efficiency varies inversely with path length). Network measures will be compared across states (waking, analgesia, anesthesia) using a repeated measures two-way analysis of variance (ANOVA) and a post hoc Tukey multi-comparison test (behavioral state as the within-subjects factor, anesthetic agent as the between-subjects factor). A p value <0.05 will be considered significant.

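### The treatment-by-time model for the connectivity maps does not fit a single fixed-order session: its interaction cannot be estimated, and it has no dose term although Aim 1 is dose dependence

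*Combined protocol and SAP*

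**What the plan says.** In the Statistical Analysis, under functional connectivity MRI, the ICA and seed-voxel maps are carried to a group analysis in which nitrous oxide effects are "estimated using a factorial model with treatment (nitrous versus placebo) and time (pre versus post) as factors". Neither *pre* nor *post* is defined.

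The design is set out under Scanning Visit in the Experimental Protocol. There is one imaging visit, in which volunteers "receive placebo (20 minutes) followed by inhaled nitrous oxide at analgesic levels (35% inhaled concentration) over 40 minutes" and then 70% for 15 minutes. A resting scan is taken before drug exposure, tasks are scanned during the placebo period, and scans are repeated at both doses. After the last dose, "recovery from anesthetic doses will occur outside of the MRI scanner as well"; the only recording described for that period is EEG.

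Data Collection adds that "Pressure pain will be applied for a continuous 6-minute period three times during the fMRI protocol".

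Aim 1 is "To identify dose-dependent changes in brain networks using fMRI studies in healthy volunteers receiving nitrous oxide". For the graph measures the plan uses a different comparison, under Network Analysis: "Network measures will be compared across states (waking, analgesia, anesthesia").

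**The concern.** A treatment-by-time factorial answers one question: is the pre-to-post change under drug larger than under placebo? It needs both scans under both treatments. The plan's Preliminary Studies describe a trial laid out that way, the pregabalin study in fibromyalgia: "Prior to and following each treatment period (drug/placebo), patients underwent fcMRI of the entire brain during rest". The present trial has no separate placebo session and no described imaging after nitrous oxide.

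Two things are at stake for the maps.

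- **Drug versus time.** The term that would separate a drug effect from drift over the session is not available. With *pre* and *post* undefined, two analysts could fit different models to the same data and both claim to follow the plan.
- **Dose.** The model has only nitrous versus placebo. Aim 1 asks about dose, and Expected Outcomes predicts low-dose changes in the links between pain regions and the default mode network, a region-to-network question of the kind the maps address. Pooling 35% and 70% could dilute effects that differ by dose. This is a risk; the plan does not predict opposite effects for the maps.

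**Working it through.** The plan gives no figure for this model, so there is nothing to reproduce. The check is whether its parameters can be estimated from the scans described.

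**Inputs**
- Model: intercept, treatment (0/1), time (0/1) and their product, so 4 parameters (fcMRI group analyses).
- Cuff runs: three in the fMRI protocol (Data Collection), taken as one each at placebo, 35% and 70%.
- Rest runs: one drug-free baseline (Scanning Visit), taken as repeated at each dose.
- Participants: 22 with complete data (Power analysis).

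**Rule.** The rank of this design equals the number of different treatment-by-time cells that contain a scan. The interaction needs all four.

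**1. Three conditions (treatment 0, 1, 1).** Each can be called pre or post, giving 2 × 2 × 2 = 8 labellings. Placebo always fills one cell. Nitrous oxide fills one cell if both doses share a label (4 labellings, rank 1 + 1 = 2) and two if they differ (4 labellings, rank 1 + 2 = 3). Rank 4 occurs in 0 of 8.

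**2. Adding subject effects.** With 22 subject effects the model has 22 + 3 = 25 columns, and its rank is 22 + (cells filled − 1).

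| Reading | Cells filled | Rank of 25 | Interaction |
|---|---|---|---|
| Placebo = pre; both doses = post | 2 | 23 | Not estimable; treatment and time are the same column |
| Baseline = placebo-pre; placebo period = placebo-post; both doses = nitrous-post | 3 | 24 | Not estimable; nitrous-pre is empty |
| Placebo = pre; 35% = nitrous-pre; 70% = nitrous-post | 3 | 24 | Not estimable; placebo-post is empty |
| Pre and post under each treatment, as in the pregabalin study | 4 | 25 | Estimable, but not the design described |

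**3. Four conditions (baseline, placebo, 35%, 70%).** There are 2⁴ = 16 labellings: rank 2 in 4, rank 3 in 8 and rank 4 in 4. All four rank-4 cases put 35% and 70% at opposite levels of time. Only one keeps time order within each treatment: baseline pre, placebo post, 35% pre, 70% post. There, time within nitrous oxide is simply dose. This set also joins a baseline rest scan to placebo-period task scans, so as described it exists for neither run type alone.

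**4. Pooling the doses (assumed effects, in arbitrary units).** The pooled effect is the mean of the two. Effects of −0.5 and +0.5 give 0; −0.5 and +0.25 give −0.125; +0.5 and +0.5 give +0.5.

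**5. A three-level condition factor.** 22 participants × 3 conditions = 66 maps. Columns: 22 + 2 = 24, rank 24. Residual degrees of freedom: 66 − 24 = 42. All three pairwise contrasts are estimable. Adding a linear period term makes 25 columns while the rank stays 24, so period cannot be separated from condition.

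**The case against.** The strongest reply has five parts.

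- **The interaction is estimable under some labellings.** True for 4 of the 16 four-condition labellings. Each needs 35% and 70% to be different times, and each mixes rest and task scans.
- **The plan never names an interaction, and main effects alone can be fitted.** With baseline as placebo-pre and the placebo period as placebo-post, the main-effects model has rank 3 of 3, so a treatment effect is estimable. That stands. But a factorial model ordinarily includes the interaction, this treatment effect pools the doses, and the time term compares a rest scan with task scans.
- **Pre and post may be two scans within each condition.** The interaction could then be estimated. Figure 1 and the earlier publications cited for the fcMRI methods could not be consulted and might clarify this. The available text describes no such pairs, three cuff runs do not allow them, and dose would still be absent. A combined visual-and-cuff task is also listed for each condition, but it is a different run type.
- **Network Analysis already covers dose.** It does for the graph measures, including the hypothesised and powered one, and this limits the finding to the ICA and seed maps. That section's between-subjects factor for anesthetic agent does not suit a one-drug study either, so only its within-subject state factor is a useful template.
- **The replacement does not separate drug from time.** Correct. Its gain is explicit dose contrasts and a defined reference scan.

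**Conclusion.** The concern holds. For each run type as described there are three conditions, and no pre/post labelling of three conditions supports the stated interaction (0 of 8). Whatever *pre* and *post* mean, the model has no dose level, so it cannot address Aim 1 for the connectivity maps.

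The conclusion rests on three readings of the text: one cuff run per condition, one drug-free rest reference repeated at each dose, and no fMRI after the 70% period. If Figure 1 shows pre and post scans within each condition, the interaction point would fall but the dose point would not.

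The scope is limited. The average path length that sets the sample size is analysed elsewhere and is unaffected. A simple nitrous-versus-placebo contrast can still be computed from the maps, though it pools the doses and is confounded with order. The likely origin of the model in an earlier two-treatment layout is inference, and nothing depends on it. This should be corrected before the maps are analysed.

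**What to change.** Replace the group model for the ICA and seed-voxel maps with one within-subject condition factor at three levels: drug-free/placebo, 35% and 70%. This matches the state factor already used for the graph measures.

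- Pre-specify three contrasts: 35% versus placebo, 70% versus placebo, and 70% versus 35%.
- Fit rest and cuff runs separately, or include a condition-by-run-type term.
- Name the drug-free scan that serves as reference for each run type.
- Keep the stated voxel and cluster thresholds.
- State as a limitation that every participant has the same order, so drug and dose effects cannot be separated from elapsed time, and that the new model does not change this.

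The cost is SAP wording only. No new scans or data are needed.

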
### Network Analysis

In terms of network properties to be analyzed, the **degree** is the number of connections a node (in this case, a given brain region) has, while the **modularity** is a measure of the extent to which the connected regions form individual functional modules. We will first investigate the characteristic modules

corresponding to different states, then quantify the modularity of the networks. High-degree **hubs** facilitate “shortcuts” of network information transmission (much like a hub airport facilitates travel shortcuts) and are identified with the measures of *centrality* in a network. The centrality of a node measures its relative ability to integrate information globally within a brain network. We will assess several centrality measures (degree centrality, closeness centrality, betweenness centrality and Eigenvector centrality) to test the robustness of the hub structure. The **average path length**, which measures the mean number of steps along the shortest paths for all possible pairs of network nodes, will be used for quantifying the **global efficiency** of brain networks (since efficiency varies inversely with path length). Network measures will be compared across states (waking, analgesia, anesthesia) using a repeated measures two-way analysis of variance (ANOVA) and a post hoc Tukey multi-comparison test (behavioral state as the within-subjects factor, anesthetic agent as the between-subjects factor). A p value <0.05 will be considered significant.

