## OBJECTIVE

The *objective of this study* is to identify the network transformations that account for the dose-dependent analgesic and sedative-hypnotic effects of the non-GABAergic anesthetic, nitrous oxide. Our *hypothesis* is that analgesic doses of nitrous oxide increase network efficiency and disrupt normal pain processing, while higher doses significantly reduce efficiency and disrupt normal conscious processing. Our *approach* is to administer two dosing levels of nitrous oxide during the acquisition of fMRI and EEG. To differentiate analgesic action of nitrous oxide from other processes, we will compare changes in brain response to noxious pressure stimuli. Our approach is *innovative* in that no study to date has acquired fMRI or EEG data to assess non-GABAergic anesthetics or to assess the relationship between analgesia and anesthesia. The *rationale* for this study is that, once completed, we will have established a detailed understanding of the therapeutic effects (analgesia and anesthesia) of a unique and understudied class of anesthetic drugs. Our *expectation* is that the knowledge derived from this study will have a positive impact by filling in a major gap in our understanding of anesthetic mechanisms and will potentially facilitate a generalized framework for anesthetic-induced unconsciousness. Furthermore, the study will provide a sophisticated network-level understanding of the relationship between the neural states of analgesia and anesthesia.

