*Training Session.* A training session with the cuff will be used to familiarize subjects with the stimuli and rating procedures and determine appropriate stimulus intensities to be used subsequently in the imaging session (see below). This can take place on the day of fMRI or during the in-clinic consent visit. During training, subjects will be maintained in a seated position in a chair with the left foot resting on a support at a slightly elevated position (but at a lower level than that of the hips, in order to facilitate blood circulation in the leg).

Testing will begin with an ascending series of pressure stimuli starting at 60 mmHg and increasing 20 mmHg increments. Ten seconds after the end of each stimulus, subjects will complete two 0-100 numerical rating scales: pain intensity (0 = “no pain”, 100 = “worst pain imaginable/extreme pain”) and pain unpleasantness (0 = “neutral”, 100 = “extremely unpleasant”). The ascending series will end when a pain intensity rating of >70/100 is obtained. Participants may also receive a continuous tonic pressure for 6 minutes to their lower leg using the cuff, and asked to rate the intensity and unpleasantness of the stimulus at certain intervals during the test, up to three times. A short break will be given between each pressure test.

This training session will have the effect of rendering subjects non-naïve to the experimental conditions in the imaging session, an aspect that might be argued to have some impact on the imaging results (particularly with regard to brain activity underlying cognitive and emotional functions). However, the training session has several advantages that outweigh these concerns: (1) identification and exclusion of individuals with unstable ratings, (2) a thorough training in the use of the rating scales, and (3) the reduced potential for developing experiment-related anxiety and head motion in the imaging session.

*Imaging session.* On the day of the imaging session, the Pain0-Pain70 pressures will be briefly recalibrated prior to scanning using procedures similar to those used during the training session.

During the fMRI scan runs, subjects will receive cuff pressures calibrated to each subject’s Pain30-50 applied for a continuous 6-min period to evaluate functional brain connectivity response to tonic deep pain. Following each cuff pain run, participants will be asked to rate the degree of pain intensity and unpleasantness on a 100-point numerical rating scale.

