### EXPECTED OUTCOMES

Based on preliminary data, we predict that administration of *low-dose* nitrous oxide will decrease network modularity and increase network efficiency, disrupting normal pain processing. Specifically, we expect to see altered relationships of key pain structures (insula, thalamus, S1 and S2) and their connections with the DMN. We expect that, as cortical activation and disorganization increase with higher doses, nitrous oxide will increase network modularity and decrease network efficiency, disrupting conscious processing of the environment in general. *Our prior study of propofol and preliminary data with 60% nitrous oxide showing decreased efficiency and increased modularity suggest the exciting possibility that GABAergic and non-GABAergic anesthetics share common network-level mechanisms to induce unconsciousness.*

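### The network ANOVA names a between-subjects agent factor that has only one level, and no written group model tests whether the change at 35% differs between cuff pain and rest

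*Combined protocol and SAP*

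**What the plan says.** All references are to the combined protocol and SAP.

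- **Network Analysis.** Network measures are compared across waking, analgesia and anesthesia by a two-way repeated-measures ANOVA with Tukey post hoc tests, taking "behavioral state as the within-subjects factor, anesthetic agent as the between-subjects factor".
- **Scanning Visit.** There is one scanning visit per volunteer, "wherein they receive placebo (20 minutes) followed by inhaled nitrous oxide at analgesic levels (35% inhaled concentration) over 40 minutes", and then 70%. No second agent and no second group are described. On the rest scan it says "Prior to drug exposure, volunteers will be given an altered states of consciousness (ASC) questionnaire followed by a baseline resting state fMRI scan". Visual, cuff and combined tasks follow in the placebo period, and the scans are then repeated at both doses.
- **Objective.** "To differentiate analgesic action of nitrous oxide from other processes, we will compare changes in brain response to noxious pressure stimuli".
- **Data Collection.** Cuff pressure in the scanner is "applied for a continuous 6-min period to evaluate functional brain connectivity response to tonic deep pain". The resting-state fcMRI paragraph covers rest and cuff data and sends both to ICA and to a seed-voxel analysis.
- **Statistical Analysis, fcMRI.** The ICA is worded for resting data. The group analysis is a "factorial model with treatment (nitrous versus placebo) and time (pre versus post) as factors".
- **Expected Outcomes.** At low dose, "nitrous oxide will decrease network modularity and increase network efficiency, disrupting normal pain processing", with altered links between insula, thalamus, S1 and S2 and the default mode network (DMN). Another agent is mentioned only as earlier work ("Our prior study of propofol").

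**The concern.** There are two separate gaps.

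First, a between-subjects factor needs at least two groups of subjects, and this design has one. The ANOVA as written does not match the design, and a reader cannot tell whether a comparison with another agent was intended.

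Second, the Objective uses painful pressure to tell analgesic action from the drug's other effects. The natural test is whether the change from placebo to 35% is different under cuff pain from what it is at rest. That is a dose-by-stimulus interaction. The two group models written out have treatment and time in one, and state and agent in the other. Neither has a term for stimulus. Moreover, the treatment factor in the connectivity model contrasts nitrous oxide with placebo and does not separate 35% from 70%, so the low-dose connectivity prediction has no comparison of its own either. What is at stake is that cuff runs are collected for this purpose without a pre-specified contrast that uses them for it.

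**Working it through.** **The plan's own figure.** The power analysis gives 22 completers for 90% power on average path length. It cannot be reproduced, because the value of d, the contrast, the test and the sidedness are not given. Solving backwards with a paired t-test at n = 22 and alpha 0.05 gives d = 0.725 (two-sided) or 0.645 (one-sided). Neither gap below depends on this figure.

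**Gap 1: degrees of freedom.** Inputs: 22 completers (power analysis), 3 states (Network Analysis), 1 agent (Scanning Visit).

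- State: 3 − 1 = 2. Error: 2 × (22 − 1) = 42.
- Agent: 1 − 1 = 0. Agent by state: 0 × 2 = 0.
- Check by design matrix: 22 × 3 = 66 rows. Subject and state terms have rank 22 + 2 = 24. Adding agent and agent by state leaves the rank at 24. Residual: 66 − 24 = 42.

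What remains is F(2,42) on state.

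**Gap 2: terms in the written models.**

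| Model | Factors | Stimulus term | 35% as its own level |
|---|---|---|---|
| fcMRI group analysis | treatment, time | none | no |
| Network ANOVA | state, agent | none | yes (analgesia) |

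Let R and C be the changes from placebo to 35% at rest and under cuff. Fitting a model to rest runs estimates R, and fitting it to cuff runs estimates C. Neither fit tests C − R, and one significant result beside one non-significant result does not test it. The quantity needed is

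C − R = (cuff − rest at 35%) − (cuff − rest at placebo).

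**Precision of that contrast.** Each subject contributes one value, so it is a one-sample t with 21 df.

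- 95% CI half-width: t(0.975, 21)/√22 = 2.080/4.690 = 0.443 SD of the contrast.
- Detectable size, two-sided 5%, noncentral t: 0.626 SD at 80% power and 0.725 SD at 90%.

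**Power for the interaction is not fixed by the documents.** As an illustration, assume that the raw interaction is as large as the powered change, that R and C have equal SDs, and that d = 0.725. Then d for the interaction is 0.725/√(2(1 − ρ)), where ρ is the correlation between R and C:

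| ρ | d for the interaction | Power at n = 22 |
|---|---|---|
| 0 | 0.513 | 63% |
| 0.25 | 0.592 | 75% |
| 0.5 | 0.725 | 90% |

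**If rest and cuff runs were pooled.** No section says that they will be, so this is only a conditional example.

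- Case A: R = −0.5, C = −0.5. Pooled (−0.5 − 0.5)/2 = −0.5; contrast 0.
- Case B: R = 0, C = −1.0. Pooled (0 − 1.0)/2 = −0.5; contrast −1.0.

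With independent run noise of SD 1 (an assumption), 20,000 simulated trials at n = 22 reject the pooled test in 61% of trials in both cases. The contrast rejects in 5% in case A and 60% in case B.

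**The case against.** The agent factor is close to editorial: software would drop it and the dose question would still be answered. That stands. A reader might infer that the main comparison is invalid, but it is not.

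The Objective does not literally call for cuff versus rest. Comparing cuff runs under nitrous oxide with cuff runs under placebo also fits its words, and the treatment factor could supply that comparison. This stands as a reading of the text. A cuff-only change, however, includes anything that happens equally at rest, so it serves the stated purpose of separating analgesia from other processes less well. The interaction is therefore an improvement that the stated purpose supports; the plan never promised it.

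A reader might also infer that the cuff data are left unanalysed, or that a general effect and a pain-dependent effect could not be distinguished at all. The documents support neither. Data Collection sends rest and cuff data to both analysis approaches, although the statistical section words its ICA for rest. Results by run type would show the two patterns separately: in the example above, case A has −0.5 at rest and case B has 0. What is missing is a formal test of the difference. The statistical section also defers to earlier publications for fcMRI methods. Those cannot be checked here, but the group model that it does write out has no stimulus term.

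**Conclusion.** The point holds in two parts of different weight.

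1. The two-way ANOVA is wrong as written. Agent and its interaction have 0 df, and the test on state survives as F(2,42) at n = 22.
2. The written models contain no stimulus term, and the connectivity model has no 35% level. A pre-specified dose-by-stimulus contrast is a cheap improvement that serves the Objective directly.

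It would be wrong to assume that the low-dose predictions are already fully covered. The network measures have the analgesia state, but the connectivity prediction has no comparison at 35%.

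Part 1 rests only on the design description. Part 2 rests on the models as written and on rest runs being available. The 0.44 and 0.63 SD figures are for a single contrast at two-sided 5% and are in SDs of the contrast, so they need no assumed effect size. Whether an effect of 0.63 SD is plausible is not known from the documents.

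**What to change.** 1. **Network Analysis.** Delete the agent factor. If the earlier propofol data were meant as a second level, say so and describe the result as a cross-study comparison.
2. **Both group models.** Replace treatment and time (fcMRI) and state and agent (network) with dose and stimulus (rest, cuff) as within-subject factors.
3. **Contrast.** Pre-specify (cuff minus rest at 35%) minus (cuff minus rest at placebo) with its 95% CI. For the pain question use one named pain-region-to-DMN connectivity measure, for example insula to DMN, which both the preliminary studies and Expected Outcomes point to. For the network analysis use average path length, the measure in the power analysis. State whether the two share one error rate. At two-sided 2.5% each, the size detectable with 90% power at n = 22 rises from 0.725 to 0.800 SD.
4. **Runs.** State which runs enter each model, and reconcile Data Collection with the rest-only wording of the ICA. Confirm that a rest run is acquired at 35%, and at 70% if that level is in the model, and that the pre-drug baseline rest scan serves as the placebo-level rest run.
5. **Optional secondary check.** Compare the cuff change with the visual-task change, reporting the difference with its CI. The visual run lasts 3 minutes against 6 for cuff, so run lengths would need matching.

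The cost is SAP wording and a little analysis, with no new scan if the rest runs are confirmed. Three limitations should be stated. Power for the interaction is not established. The fixed dose order leaves habituation to the cuff as an alternative explanation. A null interaction does not mean no analgesic effect, since the preliminary connectivity evidence itself comes from resting scans.
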